**Table 1: Subject timeline in study: For subjects recruited before January 1, 2022**

Date	Activity	Description
Baseline (Month 0)	Recruitment and enrollment	
 
Subjects will be screened for eligibility, undergo initial blood draws, and undergo randomization.
 
Subjects will be given 9-month supply of vitamin D with instructions for daily intake. Subjects will complete the intake survey via telephone or web.
 

Month 3	Wave 1	
 
Subjects will visit the lab for their follow-up Wave 1 blood draws. CRCs will call or email subjects to remind them of the lab visit as needed until the lab visit is confirmed completed.
 
Subjects will also be sent the first follow-up web-based survey via email or text message. CRCs will call and email subjects as needed to remind them to complete the survey.
 

Month 6	Wave 2	
 
Subjects will visit the lab for their follow-up Wave 2 blood draws. CRCs will call or email subjects to remind them of the lab visit as needed until the lab visit is confirmed completed.
 
Subjects will be sent the second follow-up web-based survey. CRCs will call and email subjects as needed to remind them to complete the survey. For the 6-month subject cohort, this set of labs will be their final set of labs and surveys.
 

Month 9	Wave 3	
 
Subjects in the 9-month cohort will visit the lab for their final blood draws in this wave. CRCs will call or email subjects to remind them of the lab visit as needed until the lab visit is confirmed completed.
 
Subjects will also be sent the final follow-up web-based survey. CRCs will call or text subjects to remind them to complete the survey.
 

Months 10-23	Final analysis & chart review	
 
Final analyses and reporting of the intervention effects on outcome measures will take place during this period to prepare for dissemination.
 
Chart review evaluating outcomes (e.g., hospitalization, positive COVID test)
 

		
 
For both the 6-month and 9-month cohorts, chart review will occur for 12 months after their participation
 

--	--	---

**Table 2: Subject Timeline in Study: For subjects recruited in the study on or after January 1, 2022 but before March 31, 2022**

Date	Activity	Description
Baseline (Month 0)	Recruitment and enrollment	
 
Subjects will be screened for eligibility, undergo initial blood draws, and undergo randomization.
 
Subjects will be given a bottle of vitamin D with instructions for daily intake. Subjects will complete the intake survey via telephone or web.
 

Month 3	Wave 1	
 
Subjects will visit the lab for their follow-up Wave 1 blood draws. CRCs will call or email subjects to remind them of the lab visit as needed until the lab visit is confirmed completed.
 
Subjects will also be sent the first follow-up web-based survey via email or text message. CRCs will call and email subjects as needed to remind them to complete the survey.
 
For subjects recruited March 1-31, 2022, this will be their final blood draw and survey
 

Final month (June 1-30, 2022)	Wave 2	
 
This second round of follow-up labs will apply to those recruited in January and February 2022
 
Subjects will visit the lab for final blood draws. CRCs will call or email subjects to remind them of the lab visit as needed until the lab visit is confirmed completed.
 
Subjects will be sent the second follow-up web-based survey. CRCs will call and email subjects as needed to remind them to complete the survey. For the 6-month subject cohort, this set of labs will be their final set of labs and surveys.
 

Months 4-18	Final analysis & chart review	
 
Final analyses and reporting of the intervention effects on outcome measures will take place during this period to prepare for dissemination.
 
Chart review evaluating outcomes (e.g., hospitalization, positive COVID test)
 
Chart review will occur for 12 months after this cohort's participation
 

**Table 3: Subject timeline in study: For subjects recruited after March 31, 2022 and before January 1, 2023**

Date	Activity	Description
Baseline (Month 0)	Recruitment and enrollment	
 
Subjects will be screened for eligibility, undergo initial blood draws, and undergo randomization.
 

		
 
Subjects will be given 9-month supply of vitamin D with instructions for daily intake. Subjects will complete the intake survey via telephone or web.
 

Month 3	Wave 1	
 
Subjects will visit the lab for their follow-up Wave 1 blood draws. CRCs will call or email subjects to remind them of the lab visit as needed until the lab visit is confirmed completed.
 
Subjects will also be sent the first follow-up web-based survey via email or text message. CRCs will call and email subjects as needed to remind them to complete the survey.
 

Month 6	Wave 2	
 
Subjects will visit the lab for their follow-up Wave 2 blood draws. CRCs will call or email subjects to remind them of the lab visit as needed until the lab visit is confirmed completed.
 
Subjects will be sent the second follow-up web-based survey. CRCs will call and email subjects as needed to remind them to complete the survey. For the 6-month subject cohort, this set of labs will be their final set of labs and surveys.
 

Month 9	Wave 3	
 
Subjects in the 9-month cohort (those recruited before October 1, 2022) will visit the lab for their final blood draws in this wave. CRCs will call or email subjects to remind them of the lab visit as needed until the lab visit is confirmed completed.
 
Subjects will also be sent the final follow-up web-based survey. CRCs will call or text subjects to remind them to complete the survey.
 

Months 10-23	Final analysis & chart review	
 
Final analyses and reporting of the intervention effects on outcome measures will take place during this period to prepare for dissemination.
 
Chart review evaluating outcomes (e.g., hospitalization, positive COVID test)
 
For both the 6-month and 9-month cohorts, chart review will occur for 12 months after their participation
 

**Table 4: Subject Timeline in Study: For subjects recruited in the study on or after January 1, 2023 but before March 31, 2023 (end of recruitment period)**

Date	Activity	Description
Baseline (Month 0)	Recruitment and enrollment	
 
Subjects will be screened for eligibility, undergo initial blood draws, and undergo randomization.
 
Subjects will be given a bottle of vitamin D with instructions for daily intake. Subjects will complete the intake survey via telephone or web.
 

Month 3	Wave 1	
 
Subjects will visit the lab for their follow-up Wave 1 blood draws. CRCs will call or email subjects to remind them of the lab visit as needed until the lab visit is confirmed completed.
 

		
 
Subjects will also be sent the first follow-up web-based survey via email or text message. CRCs will call and email subjects as needed to remind them to complete the survey.
 
For subjects recruited March 1-31, 2023, this will be their final blood draw and survey
 

Final month (June 1-30, 2023)	Wave 2	
 
This second round of follow-up labs will apply to those recruited in January and February 2023
 
Subjects will visit the lab for final blood draws. CRCs will call or email subjects to remind them of the lab visit as needed until the lab visit is confirmed completed.
 
Subjects will be sent the second follow-up web-based survey. CRCs will call and email subjects as needed to remind them to complete the survey. For the 6-month subject cohort, this set of labs will be their final set of labs and surveys.
 

Months 4-18	Final analysis & chart review	
 
Final analyses and reporting of the intervention effects on outcome measures will take place during this period to prepare for dissemination.
 
Chart review evaluating outcomes (e.g., hospitalization, positive COVID test)
 
Chart review will occur for 12 months after this cohort's participation
 

**Note:** While all participants will receive their final survey invitations in advance of the end of the active intervention date asking them to complete their survey by the study's end date, June 30, 2023, it is possible that some participants may not complete their surveys in time ("overdue participants"). We plan to continue to follow up with overdue participants beyond the study's end date to ensure that participants have the opportunity to complete their final survey. We will do so via multiple modalities (text, email and phone) and at different times of the day to increase response.

**Table 5: Monitoring timeline**

*Any dates specified after June 2022 are contingent on granting of second no-cost extension in Spring 2022*

Date	Activity	Description
September 2020	Clinical Advisory Committee meeting	9 faculty members of the CAC meet to create guidelines for safety testing and cutoffs, and to create the exclusion criteria
February 2021	Clinical Advisory Committee meeting	Faculty members of the CAC meet to review preliminary testing data and any clinical concerns. Will also discuss strategies for recruitment of healthy volunteers
June 2021	DSMB first meeting	DSMB meet with the PI and analysts to discuss study aims, outcomes, survey

		instruments, testing measurements, and data requests
August 2021	DSMB second meeting	DSMB meet to ensure randomization has worked: review of baseline testing and demographic characteristics by arm and review of subject complaints
December 2021	DSMB interim efficacy analysis (closed meeting)	DSMB will review longitudinal testing data by arm and conduct an interim efficacy analysis
May 2022	DSMB meeting	DSMB will meet to review trst results and PRO measurements aligned with the aims
January 2023	DSMB meeting	DSMB will meet to review test results and PRO measurements aligned with the aims.
May 2023	Final DSMB meeting	DSMB will meet to review test results and PRO measurements aligned with the aims. Will discuss dissemination strategies

## V. Location of research

The research will take place at University of Chicago Medicine at the Hyde Park campus and River East, and at Rush University (RU) on the near west side campus, Oak Park, and South Loop locations. Subjects will be recruited from all of these specified locations.

Subjects closer to UCM will pick up their vitamin D bottles at DCAM pharmacy, and subjects closer to RU will pick up their vitamin D bottles from the Rush University Professional Office building, [name]. Each bottle will contain a 9-month supply of vitamin D tablets. In the event subjects are unable to pick up their vitamin D bottles in these physical locations, bottles will be mailed to an address they provide by the UCM IDS pharmacy.

For all subjects, blood samples will be obtained by venipuncture and collected in the appropriate blood tubes. For UCM subjects, we anticipate that venipuncture and laboratory tests will be collected at the DCAM laboratory and River East laboratory and all tests will be analyzed at UCMC. We may also choose to establish temporary phlebotomy locations in additional locations for subject convenience in CCD, Mitchell, DCAM, and at Ingalls outpatient labs. If we do expand to the Ingalls phlebotomy site, we will submit an amendment to provide the required lab contracts. Laboratory tests for RU subjects will be collected by [name], site PI. For these RU subjects, samples for PTH, vitamin D, and calcium will be collected and analyzed by [name] laboratory on site. Venipuncture will be performed by research nurses or clinical research coordinators in the Allergy & Immunology Clinical Research Site of Rush University Medical Center, in Suite 739 of the Rush Professional Building. One of the tubes of blood will be transported by a research assistant to the Rush University Medical Center's Clinical Chemistry Laboratory for determination of PTH, calcium and vitamin D levels. Another tube of blood will be kept at the Allergy & Immunology Clinical Research Site for pick up/drop

off three times per week by CRCs for testing of SARS-COV-2 IgG antibodies using either the nucleocapsid or spike protein Roche Elecsys® Total Antibody test at UCM. This is to maintain internal consistency of the test across UCM and Rush, which use different assays.

Samples for Aims 4, 5, and 6, after collection will be stored in liquid nitrogen tanks in [name]'s laboratory, located on the 9th floor of KCBD on the UChicago Hyde Park campus.

Samples for Aim 7 will be stored in a lab utilized by [name] and his colleagues in the Biological Sciences Division.

Survey data will be collected by the study team at UCM's Hyde Park campus and RU's near west side campus in the W300 corridor in the Section of Hospital Medicine at UCM and in Suite 739 of the RU Professional Office Building. Data will be stored on encrypted-password protected computers, locked filing cabinets, and secured encrypted drives in these offices.

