## II. Purpose

We propose to seek to recruit participants to be randomized to low versus high (10,000 IU/day) or low versus moderate (4,000 IU/day) dose vitamin D and pool these populations for our primary analyses. The study will focus on health care workers and other individuals from Chicagoland communities with elevated risk of exposure to COVID-19. In addition to their high exposure rates to COVID-19, focusing on health care workers is also useful because they have high rates of vitamin D deficiency due to indoor work and long hours, are likely to tolerate high doses of vitamin D given their generally good health, and have ready access to monitoring for dose toxicity. In addition to HCWs, we have decided to expand our focus to include other adults in Chicagoland communities. Due to vaccine distribution in the coming months prioritizing HCWs, we want to offer the potential benefits of vitamin D in COVID-19 prevention to those who will not have prioritized access to vaccines, or choose to be vaccinated at present. **Thus, our overall aim is to compare the risks of COVID-19 in health care workers and other Chicagoland adults at increased risk of COVID-19 randomized to low (400 IU/day) vs. moderate (4,000 IU/day) or high (10,000 IU/day) dose vitamin D. Our specific aims are:**

**Aim 1:** To compare the risk of developing COVID-19 in health care workers and other Chicagoland community members at increased risk of COVID-19 randomized to low vs. moderate or high dose vitamin D. We hypothesize that moderate and high dose therapy will reduce rates of COVID-19 compared to low dose therapy because vitamin D will reduce symptomatic infection that prompts testing for COVID-19. Our primary analysis will pool subjects randomized to the moderate or high dose and compare them to low dose subjects, with secondary analyses comparing low to moderate and low to high. The design thus seeks to maximize potential to find statistically significant results between different dosages given uncertainty in subject willingness to be randomized to different doses.

**Aim 2:** To compare COVID-19 seroconversion in health care workers and other Chicagoland community members at increased risk of COVID-19 randomized to low vs. moderate or high dose vitamin D. As we suspect the main effect of vitamin D may be to decrease symptomatic disease we hypothesize that there may be little or no difference in seroconversion.

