### Procedures and Materials

Blood labs will be taken from subjects at intake, 3 months, 6 months and, if in the 9-month cohort, 9 months. If subjects are in the 2023 cohort (defined as recruited on or after January 1, 2023) blood labs will be taken from

subjects at intake, 3 months, and, if they are recruited in January or February 2023, they will have one final blood draw in June 2023. Labs for UCM subjects will be drawn at DCAM phlebotomy, River East phlebotomy, or Ingalls Hospital, depending on the location most convenient for the subject. Labs for Rush subjects will be drawn by [name] at his Rush lab.

Intake labs will measure baseline calcium and PTH levels, presence of COVID-19 antibodies, baseline vitamin D levels, and vitamin A levels. Where possible given constraints related to sample storage, analysis and available funding for free vitamin D measurement, vitamin D measurements will include free vitamin D levels measured by ELISA assay, as well as total vitamin D levels.

For Aim 7, Intake labs for UCM subjects will additionally measure vitamin D-binding protein (DBP), RAS components (Renin, Ang II, soluble ACE and ACE2), bradykinin, inflammation markers (IL-6, TNF- $\alpha$ , IL-1 $\beta$  and CRP), and SARS-CoV-2 antibodies against S-protein and N-protein.

Follow-up labs (excluding the final lab) will measure PTH levels, calcium levels, vitamin A levels for those who have high baseline vitamin A, and vitamin D levels for monitoring of the intervention's safety and outcomes, and COVID-19 antibodies for monitoring of the outcome. Records of these levels will be kept by the UCM and RU PIs and laboratories.

Final labs will measure calcium levels, vitamin D levels for monitoring of the intervention's safety and outcomes, and COVID-19 antibodies for monitoring of the outcome. Records of these levels will be kept by the UCM and RU PIs and laboratories. Final labs will not measure PTH levels. During the intervention period, our study monitors PTH levels for active participants, because primary hyperparathyroidism is a risk factor for vitamin D toxicity. Given that participants will no longer be taking study-provided vitamin D after their final lab draw, we do not believe it is medically necessary or an appropriate use of limited study resources to continue checking PTH levels with this final draw.

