Those who enroll in March 2023 will have baseline labs in March 2023 and final labs in June 2023 (3 months later). This is due to the end of study funding in June 2023. This is further specified in Section IV, Table 4 below.

Testing for calcium, PTH, and vitamin D will be done at UCM (UCMC, River East, or Ingalls) or Rush ([name]'s lab), with the site for each subject selected based on which site is most convenient for the subject. Vitamin A, which will be drawn only from UCM subjects, will be sent to an outside lab for analysis. Throughout the study period we will tell subjects about calcium, PTH and vitamin D lab results only if they suggest a safety concern for which we would like them to seek care from a medical professional. Except in the instance of a safety concern, subjects will be blinded to their vitamin A & D levels, calcium and PTH throughout the study to ensure protocol compliance. At the end of their time in the study, we will provide test results to subjects as indicated in "Study Completion Email V4". At the end of the intervention period for all participants in this protocol, we will unblind participants to their vitamin D dose assignment as indicated in "Dose Unblinding Email V1". We will do this at the end of the intervention for all participants because we, as the study team, are also currently blinded to dose assignments until the end of the intervention period for all participants. For participants who transition to participate in protocol 20-0847, unblinding will occur at the end of the intervention period for all participants in that study. Blood draws for COVID-19 antibodies will also occur at same location as their other lab draws for convenience, consolidated with other labs, but antibody testing will occur at UCM using the Roche assay for consistency given the differing ranges of different COVID-19 assays. Subjects will be instructed during the consent process to seek COVID-19 PCR testing on their own at a site convenient for them if they become symptomatic or were exposed to COVID-19, which is aligned with recommendations from CDC and IDPH. COVID-19 PCR tests will not be part of the research labs, and thus will not be paid for by the study. Subjects will self-report positive COVID-19 PCR results in the quarterly survey. Laboratory records will be monitored regularly by site PIs, Co-Investigators, and members of the DSMB and Clinical Advisory Committee for safety. Patient-reported outcome measures will be measured by a RedCap-based survey.

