
administered to subjects post-randomization over the phone or via web-based survey at baseline, depending on subject preference, and every 3 months thereafter via a web-based instrument. Subjects will be given the option to call the study team and complete the survey over the phone in reminder emails. Survey and laboratory records will be maintained and monitored by study staff on encrypted, password-protected devices in compliance with UCM and RU IRB Information Security Office standards. Electronic Medical Records will be reviewed for predictors and indicators of COVID-19 and for severity of infection if subject has had a positive COVID-19 test result.

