For our primary outcome of COVID-19 infection as measured by patient report of clinically confirmed COVID-19 (or viral PCR when available) and secondary outcomes of COVID-19 antibody seroconversion and disease severity (hospitalization, ICU stay, ventilator use, death), hazard models will be employed to assess the effect of each vitamin D dosing strategy on the outcome. We will first develop hazard ratios for between-group analyses on the primary outcome using log-rank tests, and then develop Cox proportional hazard models to model the hazard function on a set of covariates including but not limited to, moderate or high vitamin D dose, baseline vitamin D levels, age, gender, race, ethnicity, sun exposure, sleep habits, exposure of cohabitants, job type, and study site. We will also control for randomization date to adjust the underlying hazard function for COVID-19 prevalence over time. While our primary analysis will pool subjects randomized to either the moderate or high dose and compare them to low dose subjects, we will also perform secondary analyses comparing low to moderate and low to high and additional analyses that use post randomization vitamin D levels as time varying covariates. The design thus seeks to maximize potential to find statistically significant results between different dosages given uncertainty in subject willingness to be randomized to different doses. As noted above, the sample size was chosen to have at least 80% power to detect a 25% or larger decrease in the hazard of developing COVID-19 between study arms at  $p<0.05$  assuming a 30% baseline 10-month COVID incidence over the study period, in line with the 3% monthly incidence cited above. As finding that a higher dose has no effect or a paradoxical adverse effect on COVID incidence would both lead to use of a lower dose given even the small risks of higher dose vitamin D, Ruxson and Neuhauser would argue for use of a 1-sided test, resulting in 80% power to detect a 20% or larger decrease.

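### Aim 2 does not say which antibody, nucleocapsid or spike, defines seroconversion or who is at risk, so vaccination during the trial could be counted as infection

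*Combined protocol and SAP*

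**What the plan says.** The antibody test is described in three places. Section V (Location of research), writing about tubes drawn at Rush and run at UCM, provides for "testing of SARS-COV-2 IgG antibodies using either the nucleocapsid or spike protein" version of the Roche test, and gives cross-site consistency as the reason. Section III (Procedures and Materials) says that "antibody testing will occur at UCM using the Roche assay for consistency given the differing ranges of different COVID-19 assays", which names the manufacturer but not the antigen. The same section lists, for follow-up and final labs, "COVID-19 antibodies for monitoring of the outcome", again without an antigen. Both antigens are specified only in the UCM intake labs for Aim 7: "SARS-CoV-2 antibodies against S-protein and N-protein".

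The outcome itself is named but not defined. Section IX lists "secondary outcomes of COVID-19 antibody seroconversion and disease severity" among the endpoints for hazard models. For Aim 2, Section II says "we hypothesize that there may be little or no difference in seroconversion". Neither gives an antigen, a cut-off or a baseline condition.

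Vaccination falls within the trial period. Section II widens recruitment "Due to vaccine distribution in the coming months prioritizing HCWs". Sections IV, VIII and XVII also refer to vaccines being available or rolled out. Vaccination is not an exclusion criterion in Section VIII.

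**The concern.** With two tests permitted and no rule for choosing between them, the Aim 2 event depends on which test happened to be run. That would matter little if both responded only to infection. If vaccination turns the spike test positive and leaves the nucleocapsid test negative, a spike reading after vaccination records an event that is not an infection. A nucleocapsid reading at baseline followed by a spike reading later would do the same, and nothing in the plan rules that sequence out.

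Blinded randomisation should spread such events evenly over the arms, so the expected distortion is dilution toward no difference. Because Aim 2 expects little or no difference, a null result could not be told apart from misclassification. Section II also uses the contrast between Aims 1 and 2 to argue that vitamin D acts mainly on symptomatic disease. A diluted Aim 2 would appear to support that reading whether or not it is true.

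**Working it through.** **What the text settles.** Section V permits two tests, and Section III's reference to a single manufacturer does not choose between them. If both were run on every sample, the plan would still not say which result is the event or what happens when they disagree. The at-risk set is open too. Section III (Summary) describes negative baseline antibodies as part of entry, the Section VIII exclusion list has no antibody criterion, and Section XVII re-invites people earlier disqualified for a positive antibody test.

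**The plan's own figure.** There is none for Aim 2. The power statement (at least 80% for a 25% hazard reduction, 30% incidence) belongs to the primary outcome. With 1,000 per arm it implies 1,000 × (0.300 + 0.2347) ≈ 535 events and about 91% power, so it is met and is not in question.

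**Illustration of the dilution.** Inputs:
- Low-arm infection i0 = 0.30, borrowed from the primary outcome in Section IX.
- Higher-dose infection i1 = 1 − 0.70^HR. This gives 0.2347 at HR 0.75 (the primary-outcome effect, not an Aim 2 one), 0.2746 at HR 0.90 and 0.3000 at HR 1.00.
- q = share of an arm newly vaccinated after baseline × share of them turning spike-positive × share of samples read on spike. The documents do not give it, so 0 to 40% is shown. It is 0 if nucleocapsid is used throughout.
- Vaccination independent of arm and of infection, every infected person converting, everyone at risk at baseline, no dropout.

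Conversion in an arm = 1 − (1 − i)(1 − q).

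Apparent HR = ln[(1 − i1)(1 − q)] / ln[(1 − i0)(1 − q)].

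Uninfected share of low-arm converters = (1 − i0)q / conversion.

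| q | 0% | 10% | 20% | 40% |
|---|---|---|---|---|
| Low-arm conversion | 30.0% | 37.0% | 44.0% | 58.0% |
| of whom uninfected | 0% | 19% | 32% | 48% |
| Higher-dose conversion, true HR 0.75 | 23.5% | 31.1% | 38.8% | 54.1% |
| Apparent HR | 0.75 | 0.81 | 0.85 | 0.90 |
| Higher-dose conversion, true HR 0.90 | 27.5% | 34.7% | 42.0% | 56.5% |
| Apparent HR | 0.90 | 0.92 | 0.94 | 0.96 |
| Apparent HR, true HR 1.00 | 1.00 | 1.00 | 1.00 | 1.00 |

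Worked cell, HR 0.75 and q = 10%: ln(0.7653 × 0.9) / ln(0.70 × 0.9) = −0.373 / −0.462 = 0.81.

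**Cost of a less sensitive marker.** If only 80% of infections produce nucleocapsid antibody, the low arm converts at 0.8 × 0.30 = 24.0% and the higher-dose arm at 0.8 × 0.2347 = 18.8%. Two-proportion power (1,000 per arm, two-sided 0.05, HR 0.75, q = 0) falls from 91% to 81%.

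**The case against.** The harm is conditional. It needs a vaccine response that the documents do not describe, vaccination between draws, spike readings of those samples, and analysts who count them. The Section V sentence is about specimen handling, states consistency as its aim, and does not say that antigens are mixed within a participant. Recruitment was partly aimed at people with later access to vaccines, so q may be small. All of this stands, and it is why the figures are illustrations. It does not remove the gap: no section chooses the antigen, and following the plan as written permits the misclassification.

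The outcome is secondary and unpowered, and if Aim 2's hypothesis is exactly true there is no comparative bias. This also stands; only the absolute conversion rates would be inflated. But whether that hypothesis is true is what Aim 2 tests.

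A nucleocapsid-only rule is one choice among several, and its gain in power can be negligible. At HR 0.75, illustrative power is 81% with nucleocapsid detecting 80% of infections, against 79% with no fix, q = 10% and every infection detected. The gain is then in what a conversion means. A pre-stated rule using both antigens could also achieve that, provided spike positivity after vaccination is not an event.

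A reader might infer that vaccination data are not collected. The documents do not show this. Vaccination is absent from the survey items summarised in Section III and from the covariates named in Section IX, but that covariate list is open, the survey instruments are not in the file, and Section III says "Electronic Medical Records will be reviewed for predictors and indicators of COVID-19". Adjusting for randomisation date, which Section IX plans, would not correct a misclassified event.

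**Conclusion.** The point holds as a gap in the definition of a secondary outcome, and it should be fixed. That the antigen, the event and the at-risk set are undefined rests on the text alone. The consequence rests on an assumption from outside the documents (spike-based vaccines raise spike but not nucleocapsid antibody) and on an unknown q. Under the assumption, with q between 10% and 40%, a true hazard ratio of 0.75 would appear as about 0.81 to 0.90, and a true 0.90 as about 0.92 to 0.96. These are ranges, not estimates.

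Two stronger readings are not supported. A reader might infer that the trial's main result is compromised, but the primary outcome is patient-reported clinically confirmed COVID-19 or viral PCR and does not use serology. A reader might also infer that the Aim 2 comparison is biased whatever the truth, but with no true effect and vaccination independent of arm the ratio stays at 1.

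**What to change.** In Section IX, define the Aim 2 event as nucleocapsid-negative at baseline to nucleocapsid-positive at a later draw, with the same assay at both sites and all visits, and align Sections III and V with it. Restrict the Aim 2 at-risk set to baseline nucleocapsid-negative participants; this has to be stated because Section XVII brings antibody-positive people back into recruitment. Use spike results only in a sensitivity analysis limited to samples drawn before any vaccination, with vaccination dates taken from the survey or the medical records already under review, where available.

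The cost is wording, plus obtaining vaccination dates if they are not already held. Nucleocapsid is already one of the two permitted tests. Samples run only on spike must be re-run or they drop out of Aim 2, and nucleocapsid may miss some infections, at the illustrative power cost shown above. The primary analysis needs no change.
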